
Datasets required to identify vaccinated individuals
	
 • Data from the National Clinical Data Store (NCDS). Information recorded on the National Vaccine Management Tool (VMT) and GPIT system (Primary care practice medical record database) flows to the

² Stock SJ, McAllister D, Vasileiou E, *et al.* COVID-19 in Pregnancy in Scotland (COPS): protocol for an observational study using linked Scottish national data. *BMJ Open* 2020;**10**:e042813. doi: 10.1136/bmjopen-2020-042813. Available from: [COVID-19 in Pregnancy in Scotland \(COPS\): protocol for an observational study using linked Scottish national data | BMJ Open](#)

	NCDS, from where it is cleaned and then linked to the COPS data. Relevant data of interest: vaccination date, type, dose.
Datasets required to identify outcomes of interest	
 Data from a number of sources that hold pregnancy, maternal and neonatal outcome data will be brought into the COPS study dataset. Sources include: SMR01, SMR02, national linked anomaly database, SICSAG critical care admissions, NRS deaths.

3.5: Study Variables

3.5.1: Study Outcomes

Maternal, pregnancy and neonatal outcomes of interest are listed in Table 2. In our main analyses, we will assess the risk of each outcome in vaccinated women and their unvaccinated controls (i.e. classifying each woman as having the outcome or not), and will not attempt to capture any differences between the groups in the time to these events. As noted in Table 2, there are different periods of risk for each outcome (referred to as “outcome-specific follow-up period” throughout this protocol). For example, women will be considered at risk of any miscarriage from conception up to 23⁺⁶ weeks gestation, and at risk for stillbirth from 24⁺⁰ weeks gestation to the end of pregnancy. Women without an observed outcome who had not completed follow-up to the end of the follow-up period for a specific outcome in either the pre-pandemic (i.e. outcome-specific follow-up period not completed before 01 March 2020) or in the pandemic time period (i.e. outcome-specific follow-up period not completed before date of data extraction) will not be eligible for inclusion in the analysis for that outcome.

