Notes: If timing of vaccination during pregnancy is specified as 'any', this means that women vaccinated at any point from six weeks preconception to date of end of pregnancy (E) will potentially be included in the analysis dependent on the woman being followed-up to the end of the outcome-specific follow-up period. For longer term risk periods: E is date of end of pregnancy; PP is mother's postpartum period, i.e. 6 weeks following delivery (E to E+41); NN is baby's neonatal period, i.e. 4 weeks following live birth (E to E+27). The pregnancy specific maternal outcomes listed above require follow-up to the end of the postpartum period (E+41) for mothers and the end of the postnatal period (E+27) for babies.

3.5.2: Exposure

The primary exposure to be investigated in the analyses is **any** receipt of COVID-19 vaccine from six weeks before conception to the end of an outcome-specific exposure period within pregnancy (Yes/No). The exposure periods for vaccination varies for each outcome (referred to as “outcome-specific exposure period” throughout this protocol), as outlined in Table 2. For ectopic pregnancy, for example, the exposed group will include women who were vaccinated between six weeks before conception up to 2⁺⁶ weeks gestation, while for stillbirth the vaccine exposure period is extended up to the end of the pregnancy.

Subgroup analyses will be conducted where sample size permits, further stratifying women who received their COVID-19 vaccine within the outcome-specific exposure period by: (1) the number of doses received; (2) by the class of vaccine(s) received and; (3) by the type of vaccine(s) received. For the latter two subgroup analyses, we will exclude women who received multiple different classes or types of vaccine within the outcome-specific exposure period. These results will need to be interpreted with caution given that some types of vaccination will be linked to specific sub-groups of women. For example, early in the vaccination programme women who were frontline health or care workers were more likely to receive the Pfizer/BioNTech vaccine, whereas women who were clinically (extremely) vulnerable were more likely to receive the AstraZeneca vaccine. There is therefore potential for residual confounding in comparative analyses examining outcomes following receipt of specific vaccine types.

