Table 3 outlines the key information on vaccination exposure, integrated into the COPS study database from the National Services Scotland (NSS) National Clinical Data Store (NCDS).

Table 3: Exposure variables

Variable	Definition	Notes
Dose 1 received	No Yes	Exposure variable for inclusion in model Additional exposure variables for inclusion in database, descriptive analyses and any further investigation, where appropriate.
Vaccination date dose 1	dd/mm/yyyy	
Vaccine batch number 1	Unique alphanumerical code assigned to each vaccine batch	
Vaccine type 1	Pfizer/ BNT162b2 AstraZeneca/ ChAdox1nCov-19 Moderna Janssen	
Vaccination class 1	mRNA (Pfizer and Moderna) Viral Vector (AstraZeneca and Janssen)	
Dose 2 received	No Yes	
Vaccination date dose 2	dd/mm/yyyy	
Vaccine batch number 2	Unique alphanumerical code assigned to each vaccine batch	
Vaccine type 2	Pfizer/ BNT162b2 AstraZeneca/ ChAdox1nCov-19 Moderna Janssen	
Vaccination class 2	mRNA (Pfizer and Moderna) Viral Vector (AstraZeneca and Janssen)	
Dose 3 received*	No	

	Yes	
Vaccination date dose 3*	dd/mm/yyyy	
Vaccine batch number 3*	Unique alphanumeric code assigned to each vaccine batch	
Vaccine type 3*	Pfizer/ BNT162b2 AstraZeneca/ ChAdox1nCov-19 Moderna Janssen	
Vaccination class 3*	mRNA (Pfizer and Moderna) Viral Vector (AstraZeneca and Janssen)	

*Currently disaggregation by whether this was a third dose or a booster dose is not available in the COPS study database but as these data become available we will further stratify by third dose and booster dose.

3.5.3: Covariates

Covariates of importance are shown in Table 4. Note that covariate groupings will be collapsed into fewer groups where clinically appropriate to do so. Prior to statistical modelling, each covariate will be examined for collinearity.

Table 4: Covariates of interest

Covariate	Category	Notes
Deprivation Score	SIMD 1 - most deprived	
	SIMD 2	
	SIMD 3	
	SIMD 4	
	SIMD 5 - least deprived	
	Unknown	
Maternal urban-rural status	Large Urban Areas	Regrouping as binary variable to be explored.
	Other Urban Areas	
	Accessible Small Towns	
	Remote Small Towns	
	Very Remote Small Towns	
	Accessible Rural Areas	
	Remote Rural Areas	
	Very Remote Rural Areas	
	Unknown	
Maternal ethnicity	White Scottish	Regrouping into fewer categories to be explored.
	White Other British	
	White Other	
	South Asian	
	Chinese	
	Black/Caribbean/African	
	Mixed or other ethnic group	
	Unknown	

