With the pre-pandemic period being used as the baseline, there is an assumption that the pandemic has not substantially affected the outcomes of interest through, for example, changes in engagement and provision of maternity services. To investigate this, a supplementary analysis will be conducted with pregnant unvaccinated controls from the pandemic vaccination period (from 08 December 2020 to date of data extraction). In this supplementary analysis, we will exclude women (from both the vaccinated and unvaccinated group) who had any record of COVID-19 infection from six weeks preconception to the end of the outcome-specific follow-up period. However, given that there is potential for vaccination to impact on maternal, pregnancy and neonatal outcomes by changing the risks of acquiring COVID-19 and experiencing severe illness, we will also conduct a second supplementary analysis with pregnant unvaccinated controls from the pandemic. In this, we will retain both vaccinated and unvaccinated women with a confirmed record of COVID-19 infection during pregnancy and preceding the end of the outcome-specific follow-up period. For both these supplementary analyses, women who were vaccinated >6 weeks pre-conception will be included in the control group (as not vaccinated in pregnancy), however sensitivity analyses (if sample size permits) will be conducted to investigate any differences between pairs where the control is completely unvaccinated versus pairs where the control received vaccination >6 weeks pre-conception (e.g. vaccinated pre-‘pregnancy’). Additional supplementary analyses removing women who are vaccinated in the six weeks preconception will be considered for the analyses using women from the pandemic period as controls, if we observe an impact of removing these women in the primary analysis using pre-pandemic controls.

Maternal and gestational age are known to be important risk factors for adverse events in pregnancy (e.g. miscarriage strongly influenced by maternal age). Consequently, the cohorts will be matched by maternal age (± 1 years but relaxed (i.e. possibly $\pm >1$ year) at the tails of maternal age distribution as fewer individuals available for matching), and gestational age (exact match, i.e. same week however allow for relaxation of this at the tails of the gestation distribution).

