In addition, vaccinated pregnant women will also be matched by season of conception (quarter) to historical controls from the pandemic and pre-pandemic periods due to the seasonality of some outcomes. It is not necessary to do this for contemporary controls (from the pandemic vaccination period) as those pairs will be matched by calendar date (i.e. matching a vaccinated woman by maternal and gestational age, on the day of vaccination to a control of the same maternal and gestation age, on the same date).

For comparisons between vaccinated and unvaccinated matched individuals, the index date (reference point for matching maternal and gestational age, and season of gestation for analyses involving controls from historical periods only) will be the date of vaccination.

⁵ Donegan K, King B, Bryan P. Safety of pertussis vaccination in pregnant women in UK: observational study BMJ 2014; 349:g4219 doi:10.1136/bmj.g4219. Available from: <https://www.bmj.com/content/349/bmj.g4219>

The matching strategy for each of the three analyses is shown in Table 5.

Table 5: Matching strategy for each analysis of the matched cohort study

Analysis	Time period for control group*	Matched three controls to each case by:	Notes
Primary analysis	Pre-pandemic period (01 January 2015 to 29 February 2020)	
 Maternal age Gestational age Season of conception (quarter) 	
 Aim to match to three unvaccinated controls Maternal age matched by ± 1 year but relaxed at tails of maternal age distribution Gestational age matched by same week but relaxed at tails of the gestation distribution
Supplementary analysis 1	Pandemic vaccination period (from 08 December 2020 to date of data extraction), excluding cases and controls with confirmed COVID-19 between six weeks preconception to end of outcome-specific follow-up period	
 Maternal age Gestational age 	
Supplementary analysis 2	Pandemic vaccination period (from 08 December 2020 to date of data extraction), including cases and controls with confirmed COVID-19 between six weeks preconception to end of outcome-specific follow-up period	
 Maternal age Gestational age 	

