First, a model with no covariates will be fitted to calculate the unadjusted OR for the association between vaccination status and each outcomes of interest. Subsequently, we will calculate an adjusted OR for the association between vaccination status and each outcomes of interest, by adding all covariates to the model (Table 4). P-values and confidence intervals will be reported for all models. For some rarer outcomes, we will adjust our modelling approach as required (e.g. re-classification of groupings or removing insignificant covariates). Covariate pairs will be assessed for collinearity before adding to the model. For any covariate pairs that are highly correlated, only the covariate which has the biggest impact on the association between the exposure and outcome will be included in the model.

As previously described (section 3.5.2), analyses will be conducted first looking at the association between having any vaccination and outcomes, and then in sub-group analyses stratified by vaccine classes and individual vaccine types;

- Vaccine type: Pfizer, AstraZeneca, Moderna, Janssen
- Vaccine group: Pfizer and Moderna (mRNA); AstraZeneca and Janssen ((adeno)virus vector)
- Number of vaccine doses

Our main analyses will include all pregnancies/births, regardless of whether there is evidence that it was singleton or multiple, with sensitivity analyses conducted restricting to only pregnancies/births where there was no evidence it was a multiple. We often do not know whether pregnancies which end early (e.g. due to miscarriage) were singleton or multiple, hence the decision to only include pregnancies with *no evidence* of being a multiple in these sensitivity analyses.

4.5: Additional analyses

There are two further analyses that may subsequently be conducted to assess the association between vaccination and adverse outcomes, specifically:

1. We will consider using all data from the pre-pandemic period to predict the expected number of outcomes among the vaccinated pregnant women, and compare this predicted number to the observed number within the vaccinated group of women.
2. For rarer outcomes (e.g. for congenital anomalies, microcephaly), we will consider a nested case control study if signals are identified in this present matched cohort analysis but wide confidence intervals due to the small number of events negate any meaningful conclusions. This design maximises power to assess any association between vaccination and these rare outcomes.

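### The number-of-doses subgroup splits women by what happens after the matching date, which biases it for outcomes that can occur between doses, chiefly miscarriage

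*Protocol*

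**What the plan says.** Section 3.5.2 defines the primary exposure as any "receipt of COVID-19 vaccine from six weeks before conception to the end of an outcome-specific exposure period within pregnancy (Yes/No"). Where Table 2 gives the vaccination timing as any, its notes admit "women vaccinated at any point from six weeks preconception to date of end of pregnancy (E"), so a dose after the pregnancy has ended is not counted. For miscarriage the window closes at 23+6 weeks and for preterm birth at 36+6 weeks, in each case together with the risk period.

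Within that window, section 3.5.2 plans subgroups "stratifying women who received their COVID-19 vaccine within the outcome-specific exposure period by: (1) the number of doses received". Section 4.4 repeats this as "Number of vaccine doses", and section 4.3 plans tables of outcome risk by dose number.

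On matching, section 3.6 requires "gestational age (exact match, i.e. same week" (relaxed at the tails). It fixes one reference point, which for "controls from historical periods only) will be the date of vaccination". No dose is named. Two things point to the first dose in the window: the any-receipt definition of exposure, and Table 3, where the note "Exposure variable for inclusion in model" stands against receipt of dose 1.

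Section 3.5.1 classifies each outcome as present or absent and says that the main analyses "will not attempt to capture any differences between the groups in the time to these events". Section 4.4 then uses conditional or conditional multinomial logistic regression on a fixed exposure status.

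**The concern.** The number of doses a woman has received by the close of the window is not known at the date on which her controls are chosen. To be counted as a two-dose woman during pregnancy she must still be pregnant when dose 2 is given. Her controls need only be pregnant at the index date, and everything that happens to them afterwards counts. A woman who miscarries between doses is by definition a one-dose woman. This is immortal time built into the subgroup definition. Matching on gestational week at the index date does not remove it, and neither do the Table 4 covariates.

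The result would be a false contrast between dose strata: a reassuring estimate for two doses beside a worrying one for one dose. Section 6.0 sends interim and final results to the vaccine safety advisory group and potentially to the regulator, where such a pattern could be read as a dose-related safety signal.

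**Working it through.** The protocol states no figure for this bias, so there is none to reproduce. The check asks what the subgroup would show if the vaccine had no effect.

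**Inputs from the protocol (Table 2).** Background risk of miscarriage 10–20%, and of preterm birth 7%.

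**Assumed inputs, for illustration only.**
- Miscarriage: risk spread over weeks 6–24, with a hazard that is constant or falls by 15% per week; dose 1 at 8, 10 or 12 weeks; dose 2 after 3, 8 or 12 weeks and before week 24.
- Preterm birth: risk spread over weeks 24–37, with the log hazard rising by 0.25 per week; dose 1 at 20, 24 or 28 weeks; dose 2 after 3 or 8 weeks.
- Uptake *u* of dose 2 among women still pregnant: 80%, 50% or 30%.
- Index date: dose 1.

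**Formulas.** Let *r* be the risk from dose 1 to the end of the risk period (the controls' risk), *s* the probability of remaining event-free from dose 1 to dose 2, and *r₂* the risk from dose 2 onward. Then 1 − r = s(1 − r₂), and
- two-dose OR = [r₂/(1 − r₂)] / [r/(1 − r)] = s·r₂/r, the share of the controls' events that fall after the time of dose 2. It does not depend on uptake.
- one-dose OR = (1 − u × two-dose OR)/(1 − u).

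**Worked case.** Miscarriage, 10% risk, constant hazard, dose 1 at 10 weeks, interval 8 weeks. The weekly hazard is −ln(0.9)/18 = 0.00585.
- r = 1 − exp(−14 × 0.00585) = 0.0787
- s = exp(−8 × 0.00585) = 0.9543
- r₂ = 1 − exp(−6 × 0.00585) = 0.0345
- two-dose OR = 0.9543 × 0.0345/0.0787 = 0.42
- one-dose OR at 80% uptake = (1 − 0.8 × 0.4186)/0.2 = 3.33

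**The same case with other intervals and uptakes.**

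| Interval | Two-dose OR | One-dose OR, u = 80% | u = 50% | u = 30% |
|---|---|---|---|---|
| 3 weeks | 0.78 | 1.89 | 1.22 | 1.09 |
| 8 weeks | 0.42 | 3.33 | 1.58 | 1.25 |
| 12 weeks | 0.14 | 4.45 | 1.86 | 1.37 |

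**All miscarriage scenarios.** The two-dose OR runs from about 0.04 to 0.81. The lower end is 0.042 if the hazard is multiplied by 0.85 each week, and 0.046 if the log hazard falls by 0.15 each week. The one-dose OR is about 1.8–4.8 at 80% uptake, 1.2–2.0 at 50% and 1.1–1.4 at 30%.

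**Preterm birth, two-dose OR.**

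| Dose 1 at | Interval 3 weeks | Interval 8 weeks |
|---|---|---|
| 20 weeks | 1.000 | 0.928 |
| 24 weeks | 0.953 | 0.735 |
| 28 weeks | 0.865 | 0.241 |

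The first cell shows the boundary: when dose 2 precedes the risk period there is no bias.

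**After re-indexing.** If two-dose women are matched to controls still pregnant at the gestational week of dose 2, both groups carry risk *r₂* and the null OR is 1.00 by construction.

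**The case against.** The strongest objection concerns the index date. Section 3.6 names no dose, so taking it as dose 1 is an interpretation. If dose 2 were used as the index for two-dose women, their bias would disappear. That much stands. It does not rescue the subgroup, because the one-dose stratum would still collect the pregnancies that ended before dose 2 and would still be biased upward.

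Second, this is a subgroup run only where sample size permits, and Table 3 treats the later-dose variables as additional. That stands too, and it limits the severity. A reader might infer that the main safety comparison is compromised. It is not: exposure there is any dose, and with matching at the first in-window dose the classification uses nothing that happens later.

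Third, a reader might infer that every two-dose woman is guaranteed to have stayed pregnant, and that all outcomes are distorted. The documents do not support this. The window opens six weeks before conception, so both doses can precede pregnancy. For outcomes measured at birth, such as size for gestational age or Apgar score, the effect is weak or indirect.

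Fourth, the figures rest on assumed timing and uptake, and the one-dose figure is very sensitive to uptake. In addition, a woman whose first dose came more than six weeks before conception, with one further dose in pregnancy, counts as one-dose; such women may dilute the one-dose bias. This is why only ranges are given.

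Finally, the protocol does urge caution about its subgroups and plans plots of time from vaccination. However, the stated reason in section 3.5.2 is confounding by vaccine type, the plots in section 4.3 are descriptive and correct no estimate, and section 5.0 does not list this limitation. An analysis plan that is not at hand could re-index the subgroup, but the protocol as written pairs a dose count over the whole window with a single index date.

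**Conclusion.** The point holds for the number-of-doses subgroup, and for outcomes that end pregnancy or can occur between doses: chiefly miscarriage, also preterm birth and stillbirth. On the natural reading of the index date, two doses will look protective and one dose harmful with no vaccine effect. On the alternative reading, only the one-dose distortion remains.

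The direction follows from the protocol's definitions whenever dose 2 falls within the risk period. The size does not, because gestation at dose 1, dose interval and dose-2 uptake are all assumed. A reader might take the extreme values, a two-dose odds ratio near 0.05 or a one-dose odds ratio above 3, as the expected result. They are single scenarios with long intervals or high uptake; even the mildest two-dose miscarriage scenario examined, however, gives about 0.8 rather than 1. For preterm birth the null two-dose odds ratio ranges from 0.24 to no bias at all.

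This should be fixed before dose subgroups are run. It does not call the any-vaccination primary or supplementary analyses into question.

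**What to change.** In sections 3.5.2, 3.6 and 4.4, replace the split by total doses with dose-specific analyses, and state in section 3.6 which dose sets the index date.

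- **First dose:** start at the first dose in the window, whatever is received later. This largely coincides with the any-vaccination analysis.
- **Second and third dose:** use the date of that dose as the index and re-match to controls of the same age and gestational week who are still pregnant then. Where Table 2 requires a clean window, they must also be free of the event. Keep the season or calendar-date matching that applies to the control set.
- **One dose only, if wanted:** use a landmark or a time-varying dose status, because re-indexing dose 2 alone leaves this stratum biased.
- **Section 4.3:** do not present the outcome risk tables by total dose number as comparative.

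The dose dates are already held (Table 3), so no new data are needed. The cost is an extra matching run for each dose, outcome and control set, since the windows and follow-up rules are outcome-specific, together with smaller second- and third-dose sets.

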Longer term child outcomes, including immune function and infection, and neurodevelopment, will be addressed in future work as required.

Other adverse outcomes that are not specific to pregnant women, will be investigated separately for the whole population as part of wider adverse events monitoring in Scotland. If these analyses suggest any signals in the pregnant population, those outcomes would be investigated in the pregnant population using the COPS data infrastructure, as required.

Table 2: Maternal, pregnancy and neonatal outcome measures for monitoring of safety of COVID-19 vaccination in pregnancy

Outcome measure	Definition	Primary or secondary outcome?	Clean window requirement to identify incident cases	Timing of vaccination to be included	Post vaccination risk period to be examined	Estimated background risk of outcome (%)
Maternal outcomes						
Hypertensive disorders of pregnancy	See ICD10 code list. Note that hypertensive disorders can only be diagnosed at >20 weeks.	Primary	No prior record in this pregnancy	Any	Up to E plus PP	10.0
Venous thromboembolism	See ICD10 code list	Primary	No prior record in this pregnancy	Any	Up to E plus PP	0.15
Pregnancy-related bleeding	See ICD10 code list	Primary	No prior record in this pregnancy	Any	Up to E plus PP	30.0 (for postpartum haemorrhage)
ICU admission or death (any cause)	ICU admission as identified on SICSAG record Death from any cause	Primary	None (but exploration to be undertaken of reasons for any pre-vaccination ICU admission where these are documented)	Any	Up to E plus PP	Unknown
Pregnancy outcomes						
Miscarriage	Miscarriage at <24 completed weeks gestation	Primary	None	Up to 23w+6d gestation	Up to 23+6 gestation	10.0 – 20.0

• First trimester miscarriage	Miscarriage at <14 completed weeks gestation	Secondary	None	Up to 13+6 gestation	Up to 13+6 gestation	Unknown
• Second trimester miscarriage	Miscarriage at 14-<24 completed weeks gestation	Secondary	None	Up to 23+6 gestation	14+0 to 23+6 gestation	Unknown
Ectopic pregnancy	Ectopic pregnancy ending at any gestation	Primary	None	Up to 2+6 gestation	Up to E	1.0
Stillbirth	Spontaneous fetal loss at ≥24 completed weeks gestation Any cause of fetal death Losses related to termination of pregnancy excluded	Primary	None	Any	24+0 to E	0.4
Baby outcomes (live births only unless otherwise stated)						

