Any congenital anomaly (relevant pregnancy outcome only)	Any major congenital anomaly as defined by EUROCAT (including live born babies diagnosed at <28 days of age and affected pregnancies resulting in spontaneous loss at ≥20 weeks or termination of pregnancy at any gestation)	Primary	None	Up to 9+6 gestation	At E plus NN	2.7
• Any non-genetic congenital anomaly (relevant pregnancy outcome only)	Any major congenital anomaly as defined by EUROCAT, excluding anomalies with known underlying genetic basis as per standard EUROCAT rules (including live born babies diagnosed at <28 days of age and affected pregnancies resulting in spontaneous loss at ≥20 weeks or termination of pregnancy at any gestation)	Secondary	None	Up to 9+6 gestation	At E plus NN	2.3
Microcephaly	Congenital microcephaly (i.e. present at birth) OFC on delivery record <2SD below	Primary	None	Any	At E	2.0

	mean for sex and gestation at delivery by WHO-UK90 growth reference Babies with anencephaly excluded					
• Severe microcephaly	Congenital microcephaly (i.e. present at birth) OFC on delivery record <3SD below mean for sex and gestation at delivery by WHO-UK90 growth reference Babies with anencephaly excluded	Secondary	None	Any	At E	0.4
Preterm birth	Delivery at <37 completed weeks gestation	Primary	None	Up to 36+6 gestation	Up to 36+6 gestation	7.0
• Very preterm birth	Delivery at <32 completed weeks gestation	Secondary	None	Up to 31+6 gestation	Up to 31+6 gestation	1.0
Spontaneous preterm birth	Delivery at <37 completed weeks gestation following P-PROM or spontaneous onset of labour	Primary	None	Up to 36+6 gestation	Up to 36+6 gestation	4.0
• Spontaneous very preterm birth	Delivery at <32 completed weeks gestation following P-PROM or spontaneous onset of labour	Secondary	None	Up to 31+6 gestation	Up to 31+6 gestation	0.6
Small for gestational age	Birthweight <10th centile by WHO-UK90 growth reference	Primary	None	Any	At E	10.0
• Very small for gestational age	Birthweight <3rd centile by WHO-UK90 growth reference	Secondary	None	Any	At E	3.0
Low Apgar score	5 min Apgar <7	Primary	None	Any	At E	1.5
• Very low APGAR score	5 min Apgar <4	Secondary	None	Any	At E	0.5
Neonatal death	Death from any cause	Primary	None	Any	E plus NN	0.2
Extended perinatal mortality (total births)	Stillbirth or neonatal death from any cause	Primary	None	Any	Up to E plus NN	0.6

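### Dropping women who receive a second vaccine class or type within the exposure period can bias product-specific odds ratios upward, mainly for miscarriage; the size depends on a switching share the protocol does not give.

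*Protocol*

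**What the plan says.** Section 3.5.2 plans subgroups by number of doses, by vaccine class and by vaccine type, if numbers allow. For class and type, "we will exclude women who received multiple different classes or types of vaccine within the outcome-specific exposure period".

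The exposure period starts six weeks before conception and ends at an outcome-specific point given in Table 2:
- **Miscarriage** ("Miscarriage at <24 completed weeks gestation"): the window closes at 23+6 weeks.
- **Preterm birth** ("Delivery at <37 completed weeks gestation"): it closes at 36+6 weeks.
- **Outcomes with timing Any:** "women vaccinated at any point from six weeks preconception to date of end of pregnancy (E) will potentially be included". Section 3.5.2 gives stillbirth as its example: "while for stillbirth the vaccine exposure period is extended up to the end of the pregnancy".
- **Ectopic pregnancy:** the exposed group is "women who were vaccinated between six weeks before conception up to 2⁺⁶ weeks gestation".
- **Congenital anomaly:** the window closes at 9+6 weeks.

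Section 3.6 sets the index date for matching at the date of vaccination, without saying which dose counts when there are several. Table 3 records date, type and class for up to three doses and marks receipt of dose 1 as the exposure variable for the model. Section 3.5.1 treats outcomes as yes or no, not as times to event.

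**The concern.** Whether a woman stays in a product subgroup depends on a dose given after the one that made her exposed. That later dose can fall in the window only while the pregnancy continues. Take a woman given one product at 6 weeks who miscarries at 9 weeks: she is kept. If she is still pregnant at 18 weeks and then receives a different product, she is removed, and her event-free follow-up to that point goes with her. Unvaccinated controls are not thinned in this way.

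Nothing else in the protocol corrects this. Matching on gestational week happens before the selection. Dropping a switcher's controls along with her does not help, because those controls were not selected on their outcome and she was. With binary outcomes there is no censoring or splitting of follow-up at a switch. The caution in section 3.5.2 concerns which women received which product, and the limitations in section 5.0 do not cover this selection.

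Product-specific odds ratios are what a reader would use to judge whether one vaccine carries a risk in pregnancy, and section 6.0 foresees sharing a signal with the regulator. An artefact towards harm therefore matters even in a subgroup analysis.

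**Working it through.** The protocol gives no figure for this bias and no switching share, so there is nothing to reproduce. Everything below assumes no true vaccine effect and a range of switching shares.

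**1. Closed form.** Let p be the risk of the event. Let s1 and s0 be the probabilities that a woman with and without the event, respectively, has a recorded switch in the window. After the exclusion the odds among retained women are p(1 − s1) / [(1 − p)(1 − s0)]. The control odds are p / (1 − p). The ratio is

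OR = (1 − s1) / (1 − s0),

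which exceeds 1 whenever women with the event have less opportunity to switch (s1 < s0).

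**2. Ceiling.** If a share w of women would switch were the pregnancy to continue, then s0 is at most w and s1 at least 0, so OR is at most 1 / (1 − w):
- w = 1%: 1/0.99 = 1.01
- w = 5%: 1/0.95 = 1.05
- w = 10%: 1/0.90 = 1.11
- w = 30%: 1/0.70 = 1.43

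**3. Simulation.** Some women with the event do switch first, and some women without it run out of window. A simulation of 2,000,000 pregnancies allows for both. Its inputs are assumptions: event timing; first dose uniform from 4 weeks before gestational week 0 to one week before the window closes; and a switch either 8–12 or 12–26 weeks after the first dose. Retained women are compared with unselected controls matched on gestational week at first dose. The ranges cover the two switch intervals.

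| Would-be switchers | Miscarriage OR | Stillbirth OR | Preterm birth OR |
|---|---|---|---|
| 1% | 1.01 | 1.00 | 1.00 |
| 5% | 1.03–1.04 | 1.01 | 1.00 |
| 10% | 1.06–1.08 | 1.02 | 1.01 |
| 30% | 1.20–1.28 | 1.07–1.08 | 1.03 |
| 50% | 1.39–1.63 | 1.15–1.17 | 1.06–1.07 |

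The miscarriage values in the 1–30% rows lie at or below the ceilings in step 2.

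**4. One cell by hand, and why matching does not help.** Take miscarriage, 30%, switch at 8–12 weeks. The retained risk is 0.0739 and the matched control risk 0.0586, so OR = (0.0739/0.9261) / (0.0586/0.9414) = 0.0798/0.0622 = 1.28. Against all vaccinated women before exclusion (risk 0.0652), the ratio is only 0.0798/0.0697 = 1.14. That agrees with the closed form using the simulated shares s1 = 0.084 and s0 = 0.199: 0.916/0.801 = 1.14. The matched figure is larger because the exclusion leaves relatively more women first vaccinated late, when the remaining miscarriage risk is lower, and their matched controls share that lower risk.

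**5. Outcomes barely affected.** These were reasoned, not simulated. The ectopic window closes at 2+6 weeks, when almost every pregnancy is still ongoing. The anomaly window closes at 9+6 weeks, and the definition counts live births, spontaneous losses from 20 weeks and terminations, so few affected pregnancies end before it closes.

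**6. After the fix.** If no woman is excluded for a later dose, s1 = s0 = 0 and OR = 1.00.

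**The case against.** The strongest counter-argument is that switching may be rare. The background text before section 2.0 says that a woman who had a first dose before pregnancy should finish with the same product where possible. Exclusion also requires two different products inside the window; an earlier product given more than six weeks before conception does not count. At 1–5% would-be switching the miscarriage odds ratio is only 1.01–1.04. This stands, and it limits the size of the point. It does not settle it: the protocol found switching likely enough to write a rule for it, and Table 3 records third doses ("as these data become available we will further stratify by third dose and booster dose").

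A reader might go further than the documents allow. One could assume that 20% of women without a miscarriage and 2% of women with one switch, and quote 0.98/0.80 = 1.22 as the bias; or assume 30% and 20% for term and preterm births and obtain a risk ratio of 1.13. The arithmetic is right, but the shares are invented. The preterm contrast is also too wide: the window closes at 36+6 for everyone, so term pregnancies gain no switching time after that, and the simulation gives about 1.03.

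It is also fair to say that restricting to one product answers a legitimate question, exposure to that product alone, and that these are subgroup analyses already flagged for caution. That supports keeping the restricted analysis as a secondary view. It does not support making it the main product-specific estimate, because the flagged caution concerns confounding. The time-to-outcome plots in section 4.3 would not correct the selection.

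**Conclusion.** The point holds as a possible upward bias in the class and type subgroups, mainly for miscarriage. The direction follows from the rule itself, provided first exposure starts follow-up. Section 3.6 does not name the dose, but Table 3 supports that reading.

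The size is unknown. It is negligible to small at 1–10% would-be switching (miscarriage odds ratio 1.01 to 1.08). At 30% (odds ratio 1.20–1.28, risk ratio 1.19–1.26) it is comparable to the relative risk of 1.2 used as a scenario in Table 6. Stillbirth is affected less and preterm birth only slightly. These figures rest on assumed event timing, dose timing and switch intervals, and on a simple binary comparison instead of the multinomial model that section 4.4 plans for miscarriage and stillbirth.

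The documents do not support saying that any product will look harmful, nor that the main result is in doubt. The any-vaccine comparison does not use this exclusion.

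**What to change.** In sections 3.5.2 and 4.4:

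1. State that the index date is the first dose within the outcome-specific exposure period.
2. Define vaccine class and type by that dose.
3. Keep women who later receive a different product in the subgroup of their first in-window dose.
4. Report, for each outcome and product, how many women switched, split by whether the outcome occurred.

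The single-product-only analysis may stay as a sensitivity analysis, with the selection described above stated beside it.

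The cost is a few sentences; dates, types and classes by dose are already in Table 3. The drawback is a slightly different question: the estimate becomes one for starting with a product, and some women in the subgroup will also have had a later dose of another. The switching counts let the reader judge how much that matters.
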